12.3. Analysis Sets

The following analysis sets will be evaluated and used for presentation of the data:

- Intend-to-Treat Analysis Set (ITT): All subjects who were randomized. Subjects will be classified according to the assigned treatment arm. The ITT will be used for the primary efficacy analyses, and is the default analysis set unless otherwise specified.

- Safety Analysis Set (SAS): All subjects who received at least one dose of study treatment. Subjects will be classified according to the treatment received. The SAS will be the primary set for the analysis of safety data, unless otherwise specified.
- Crossover Set (COS): A subset of subjects initially assigned to receive placebo who crossed over and received AG-120.
- Per-Protocol Set (PPS): All subjects in the ITT who had no major protocol violations. Additional efficacy analyses may be produced using the PPS. Rules for major protocol violations will be specified in the statistical analysis plan (SAP).
- Pharmacokinetic Analysis Set (PAS): All subjects who have at least 1 blood sample post-dose providing evaluable PK data for AG-120.

12.4. Randomization and Stratification

Eligible subjects will be randomized in a 2:1 ratio to receive AG-120 or placebo, stratified by number of prior therapies (1 vs 2). The randomization scheme will be generated by an independent statistical group. The randomization assignment will be implemented by an interactive web response system (IWRS).

12.5. Disposition

A tabulation of the disposition of subjects will be presented by treatment arm, including the number randomized, the number treated, the reasons for treatment discontinuation, and the reasons for study discontinuation. Entry criteria and protocol deviations will be listed.

12.6. Baseline Evaluations

Demographic and baseline disease characteristic data will be summarized by treatment arm. Data to be tabulated will include sex, age, and race and ethnicity, as well as disease-specific information.

12.7. Efficacy Analyses

Response to treatment will be assessed by the site Investigators and by the IRC using RECIST v1.1 (see Section 10.7).

To control the overall Type I error rate at the 5% level, the fixed sequence testing procedure (Westfall and Krishen 2001) will be used to adjust for multiple statistical testing of the primary and selected secondary efficacy endpoints. These endpoints will be tested in the following order:

- PFS based on IRC
- OS
- ORR based on IRC

No adjustment to the α level will be made for the other analyses.

12.7.1. Analysis for the Primary Endpoint

The primary endpoint of PFS is defined as the time from the date of randomization to the date of first documentation of disease progression as determined by the IRC per RECIST v1.1 or death due to any cause, whichever occurs first.

Subjects without documentation of disease progression or death at the time of the primary analysis of PFS will be censored at the date of the last response assessment prior to the start of alternate therapy. If disease progression or death is documented after 1 single missing response assessment, the actual event date of disease progression/death will be used for the PFS event date. If disease progression is documented after 2 or more missing response assessments, the PFS time of these subjects will be censored at the date of the last response assessment (CR or PR or SD) prior to 2 or more missing response assessments. Detailed censoring rules will be specified in the SAP.

The primary efficacy analysis will be the comparison of the distribution of PFS between the two treatment arms using a log-rank test stratified by the randomization stratification factor at one-sided 2.5% level of significance. Assuming a proportional hazard model for PFS, the null hypothesis will be tested:

$$H_{01} \text{ (null hypotheses): } \Theta_1 \geq 0 \text{ vs. } H_{a1} \text{ (alternative hypotheses): } \Theta_1 < 0$$

where Θ_1 is the log hazard ratio of PFS in the AG-120 (investigational treatment) arm vs. placebo (control) arm.

A Cox regression model stratified by the randomization stratification factor will be used to estimate the HR of PFS comparing the AG-120 arm with the placebo arm, along with the 95% CI.

Kaplan-Meier estimates of PFS, including estimates of the median and other quantiles, as well as individual time points (eg, 3-month, 6-month, and 12-month rates), will be presented for each treatment arm. Patterns of censored data will be examined between the treatment arm and placebo arm by summarizing the number of PFS events that are censored and by tabulating the reasons for censored observations.

There will be no interim analysis for PFS. The analysis of PFS will be performed when 131 Investigator-assessed PFS events have occurred, expected at approximately 32 months after the first subject is randomized in the study. The primary analysis of PFS will be based on IRC response assessments.

Sensitivity analyses for PFS may include but are not limited to the tests listed below. PFS may be analyzed using:

1. Stratified log-rank test using the PPS based on Investigator assessments;
2. Stratified log-rank test using the PPS based on IRC assessments;
3. Unstratified log-rank test using the ITT based on Investigator assessments;
4. Unstratified log-rank test using the ITT based on IRC assessments.

Other sensitivity analyses for PFS may be conducted and will be specified in the SAP.

Subgroup analyses will be performed on each level of the stratification factor. The analyses will include Kaplan-Meier summaries, unstratified log-rank tests and HRs (together with associated 95% CIs) from Cox regression models. Other subgroup analyses for PFS, including but not limited to locally advanced vs. metastatic cancer, may be conducted and will be specified in the SAP.

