
Statistical methods:
 
The primary objective of the study is to demonstrate improvement in PFS by IRC assessment for subjects receiving treatment with AG-120 compared to subjects receiving placebo. Assuming a hazard ratio (HR) of 0.5 for PFS (equivalent to a median PFS of 3 months in the placebo arm versus 6 months in the AG-120 arm, assuming an exponential distribution), a total of 131 PFS events are required to provide 96% power at a 1-sided alpha of 0.025 level of significance to reject the null hypothesis (see Section 12.7.1) using a stratified log-rank test. Based on this, a total of approximately 186 subjects will need to be randomized in a 2:1 ratio to the AG-120 and placebo arms, respectively, assuming approximately a 22% dropout rate, an approximate 26-month randomization period, and an additional 6-month follow-up for PFS after the last subject is randomized.
 
Progression-free survival is defined as the time from the date of randomization to the date of first documentation of disease progression or death due to any cause, whichever occurs first. Subjects without documentation of disease progression or death at the time of the primary analysis of PFS will be censored at the date of the last response assessment prior to the start of alternate therapy. Detailed censoring rules will be specified in the Statistical Analysis Plan (SAP). The primary analysis of PFS will be based on IRC response assessments. PFS based on response assessment determined by the Investigator will also be analyzed. Time from first dose of study drug to second documented disease

progression (or death) will be calculated for subjects who cross over from the placebo arm to the AG-120 arm (PFS2).

Kaplan-Meier estimates of PFS will be presented for each treatment arm, including estimates of the median and other quantiles, as well as individual time points (eg, 3-month, 6-month, and 12-month rates). The HR of PFS with 95% confidence interval (CI) comparing AG-120 with placebo will be estimated from a Cox proportional hazards model. The log-rank test will be used to compare PFS between the 2 treatment arms.

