7. INVESTIGATIONAL PLAN

7.1. Overall Study Design

This is a Phase 3, multicenter, randomized, double-blind, placebo-controlled efficacy and safety study of orally administered AG-120 in subjects with advanced cholangiocarcinoma (nonresectable or metastatic). Subjects, all personnel involved in the evaluation of subjects' response to treatment (eg, Investigators, study coordinators, study pharmacists), and designated Sponsor team members will be blinded to study treatment until documented disease progression. Subjects are required to have a histologically consistent diagnosis of IDH1 gene-mutated cholangiocarcinoma that is not eligible for curative resection, transplantation, or ablative therapies. Subjects must have documented progression of disease and have received treatment with at least 1 but not more than 2 prior treatment regimens for advanced disease (nonresectable or metastatic). At least 1 of the prior regimens must have included gemcitabine or 5-FU. Systemic adjuvant chemotherapy will be considered a line of treatment if there is documented disease progression during or within 6 months of completing the therapy, with Sponsor approval.

A total of approximately 186 subjects will be randomized in a 2:1 ratio to the AG-120 and placebo arms, respectively, stratified by number of prior therapies (1 vs. 2). The enrollment duration will be approximately 26 months, assuming an initial 5 subjects per month enrollment rate for the first 6 months and 8 subjects per month thereafter. The primary analysis of PFS will occur once 131 PFS events have been determined by Investigator assessment (approximately 6 months after the last subject is randomized). OS will be analyzed twice, once at the time of PFS primary analysis and once at the occurrence of 150 OS events (approximately 24 months after the last subject is randomized).

An independent data monitoring committee (IDMC) will review the safety data on a regular basis to ensure the safety of treatment and proper conduct of the study. The first interim safety review meeting will be conducted when approximately 20 subjects have completed 2 cycles of therapy or have discontinued earlier; thereafter, meetings will be conducted every 3-6 months or on an ad hoc basis. No formal interim analysis for efficacy will be conducted before the primary analysis.

Each subject's course of treatment will be comprised of the following periods:

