12.2. Sample Size Estimation

A total of approximately 186 subjects will be needed for the study.

The primary objective of the study is to demonstrate the improvement in PFS by IRC assessment for subjects receiving treatment with AG-120 as compared to subjects receiving placebo. Assuming a hazard ratio (HR) of 0.5 for PFS (equivalent to a median PFS of 3 months in the placebo arm versus 6 months in the AG-120 arm, assuming an exponential distribution), a total of 131 PFS events are required to provide 96% power at a 1-sided alpha of 0.025 level of significance to reject the null hypothesis (Section 12.7.1) using a stratified log-rank test. Based on this, a total of approximately 186 subjects will need to be randomized in a 2:1 ratio to the AG-120 and placebo arms, respectively, assuming approximately a 22% dropout rate, an approximate 26-month randomization period, and an additional 6-month follow-up for PFS after the last subject is randomized. Therefore, the primary analysis of PFS will occur at approximately 6 months after the last subject is randomized.

Overall survival will be analyzed twice, once at the time of the final analysis for PFS and once at the occurrence of 150 OS events (final analysis for OS, which will occur at approximately 24 months after the last subject is randomized). Assuming an HR of 0.67 for OS (median OS of 8 months in the placebo arm vs. 12 months in the AG-120 arm, assuming an exponential distribution), a total of 150 OS events will provide 64% power at a 1-sided alpha of 0.025.

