8. EFFICACY ANALYSIS

For PFS, best overall response (BOR), ORR, DOR and other endpoints based on progression and/or response status, the primary analyses will be based on the independent central review by IRC. The endpoints based on Investigator assessment will be used as secondary analyses. Efficacy data after crossover will be analyzed separately.

After unblinding at local PD per Investigator assessment, subjects on AG-120 are allowed to stay on AG-120 if the treating Investigator deems they are clinically benefiting. The IRC will read all scans up to the discontinuation of AG-120. Subjects on placebo will no longer stay on placebo after radiographic disease progression and unblinding, hence no further scans will be read by IRC beyond the initial locally assessed disease progression imaging time point. Because of that, there is a potential systematic bias that subjects on the AG-120 arm could have PD called by IRC later than the locally assessed PD date; however, subjects on the placebo arm would systematically be censored by IRC analysis at the time of local PD if not concordant with local PD. To alleviate the potential imbalance between two arms, IRC assessments after the local PD from both arms will be excluded from the primary analysis of scan-related endpoints per IRC read. A sensitivity analysis by including all the scans read by IRC will be conducted.

All efficacy analyses will be based on the ITT set unless stated otherwise. If analyses are performed on more than one analysis set, the analyses on the ITT set will be considered primary. For each period, once the PD occurred, or the new anticancer therapy was initiated, all the subsequent tumor/response assessments will not be included in the tumor/response related summary analyses, but it will be included in the data listings.

Data after crossover (such as PFS) will be analyzed in a similar manner.

Listings for all efficacy endpoints will be provided.

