8.1. Progression-Free Survival (PFS)

8.1.1. Primary Analyses of PFS

The primary analysis of PFS will be based on IRC assessment for ITT set.

Progression-free survival (PFS) is defined as the time in months from the randomization date to the date of the first documentation of disease progression as determined by the IRC per RECIST v1.1 or death due to any cause, whichever occurs first.

$$\text{PFS} = (\text{Earliest Date of Disease Progression or Death} - \text{Randomization Date} + 1) / 30.4375.$$

The approach regarding handling of missing response assessments and censoring is presented in [Table 1: Handling of Missing Response Assessment and Censoring for the Primary Analysis of PFS](#).

A stratified log-rank test (one-sided) will be used to compare PFS of the AG-120 arm against the placebo arm at the time when 131 investigator-assessed events have occurred, with the one-sided significance level controlled at 0.025. The HR (AG-120/placebo) and the corresponding 2-sided 95% confidence interval (CI) will be estimated using a stratified Cox regression model. For both the stratified log-rank test and stratified Cox regression model, the strata will be those used for stratified randomization, that is, the number of prior lines of therapy at randomization.

Number of subjects with events, types of events (progression or death), and number of subjects censored, number of subjects for each reason of censoring, Kaplan-Meier estimates, and 95% CIs for the 25th percentile, median, and the 75th percentile for PFS will be presented by treatment group. Probabilities of event free at selected time points, such as 3-month, 6-month, 9-month, and 12-month, will be presented by treatment arms. Kaplan-Meier curves of PFS will be provided for each treatment arm with the number of subjects at risk over time included.

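### Does setting the cutoff at 131 Investigator-assessed events leave the IRC primary test short of its stated 96% power?

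*Protocol*

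**What the plan says.** Protocol 12.2 opens with "The primary objective of the study is to demonstrate the improvement in PFS by IRC assessment" and then says that "a total of 131 PFS events are required to provide 96% power at a 1-sided alpha of 0.025". The Synopsis and SAP 5 carry the same pair of statements. The power sentence does not say who assesses the 131 events.

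The timing of the analysis does name the assessor. Protocol 7.1 has "The primary analysis of PFS will occur once 131 PFS events have been determined by Investigator assessment" and Protocol 12.7.1 has "The analysis of PFS will be performed when 131 Investigator-assessed PFS events have occurred". SAP 8.1.1 places the stratified log-rank test "at the time when 131 investigator-assessed events have occurred". The Synopsis (end of its statistical methods), Protocol 12.1 and SAP 4 agree. Protocol 12.7.1 and SAP 8.1.1 also say openly that the test itself uses IRC assessments.

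SAP 8 adds a rule that bears on the count: "IRC assessments after the local PD from both arms will be excluded from the primary analysis of scan-related endpoints per IRC read". Its stated reason is an imbalance between arms. IRC reads would continue past local progression for patients who stay on AG-120, whereas "subjects on the placebo arm would systematically be censored by IRC analysis at the time of local PD if not concordant with local PD". SAP 8.1.2 plans a summary of agreement between the two assessors, by arm and overall. No planning value for that agreement appears in either document.

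**The concern.** The information in a log-rank test is the number of events that enter it. Here one assessor's count fixes the cutoff and the other assessor's events enter the test. A local progression that the IRC has not called by that scan counts toward the 131, but under SAP 8 it cannot become an IRC progression event later. If the IRC count falls short, the test has less than 96% power, and IRC PFS is the gate to the OS and ORR tests. The planning sections can be read as promising 96% for a test that may have fewer events than they name, with nothing to show how many fewer.

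**Working it through.** **The plan's own figure.** Inputs from Protocol 12.2: hazard ratio 0.5, 2:1 allocation, one-sided alpha 0.025, 131 events. Schoenfeld's formula with allocation shares 2/3 and 1/3 is

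power = Φ(√(d × 2/9) × ln 2 − 1.960)

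For d = 131: √(131 × 2/9) × 0.6931 = 3.740; 3.740 − 1.960 = 1.780; power = 96.2%. The stated 96% is reproduced.

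**Power by number of IRC events, same formula.**

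| IRC events | Power |
|---|---|
| 131 | 96.2% |
| 124 | 95.3% |
| 118 | 94.4% |
| 110 | 92.9% |
| 105 | 91.7% |
| 99 | 90.2% |
| 74 | 80.3% |

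Power is at least 90% down to 99 events (24% fewer than 131) and at least 80% down to 74 (44% fewer).

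**How many IRC events might there be?** The documents give no inputs for this, so the following are assumptions:

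- D = 13.1 of the 131 Investigator events are deaths (10%), which leaves 117.9 local progressions.
- c = share of local progressions the IRC calls by the same scan, 75% to 95%.
- q = share of the remaining local progressions followed by a death that still counts as a primary PFS event (inside the 95-day gap and before other systemic therapy, SAP Table 1), 0 to 30%.
- r = share of the other 186 − 131 = 55 patients with progression by IRC only, 0 to 10%.

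d = D + c × 117.9 + q × (1 − c) × 117.9 + r × 55

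| c | q | r | IRC events | Power |
|---|---|---|---|---|
| 0.75 | 0 | 0 | 101.5 | 90.9% |
| 0.75 | 0.30 | 0.10 | 115.9 | 94.0% |
| 0.85 | 0 | 0 | 113.3 | 93.6% |
| 0.85 | 0.15 | 0.05 | 118.7 | 94.5% |
| 0.85 | 0.30 | 0.10 | 124.1 | 95.4% |
| 0.95 | 0 | 0 | 125.1 | 95.5% |
| 0.95 | 0.30 | 0.10 | 132.4 | 96.4% |

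The middle row worked out: 13.1 + 0.85 × 117.9 + 0.15 × 0.15 × 117.9 + 0.05 × 55 = 13.1 + 100.2 + 2.7 + 2.75 = 118.7 events. Power there is 94.5%, which is 1.7 points below 96.2%. The lowest value in the grid needs 75% agreement with no counted deaths and no IRC-only progressions, all together. The last row exceeds 131, so even the direction is not fixed by the documents.

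**The case for a change.** The strongest case for acting is that the figure and the test do not share a count, and that the sponsor knew why they might differ. SAP 8 uses the discordance mechanism to deal with bias between arms, yet SAP 5 repeats the power statement without it. The 22% dropout allowance does not answer this: it links 186 patients to 131 events, and extra patients cannot raise the IRC count once the cutoff is tied to Investigator events. The offset from deaths may also be weak. SAP 8 analyses efficacy data after crossover separately, so a death after a discordant placebo patient crosses over may not count. Finally, the cushion depends on the design effect: at an assumed hazard ratio of 0.6, power is 78.7% with 131 events and 69.4% with 105.

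Most of this stands as description. The counts can differ, a shortfall is more likely than an excess, and dropout does not cover it. It does not amount to a defect. Setting the death offset to zero at 85% agreement still leaves 93.6%. In the 0.6 example, the weaker effect alone costs 17.5 points (96.2 − 78.7) before any event is lost; that is a risk in the effect assumption and exists with either assessor's count. The documents also do not hide the arrangement: the Investigator basis of the 131 is stated in the Synopsis and in five other sections, in Protocol 12.7.1 alongside the statement that the test uses IRC reads.

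**Conclusion.** No change is needed. The 96% is arithmetically right for 131 events, and the power sentence does not claim that the IRC will supply exactly that number. What is missing is a planning assumption about agreement between assessors. The documents give no value for it, so the sponsor would have to choose one without a source in the plan. At a hazard ratio of 0.5 the loss is about 1 to 3 points if agreement is 85%, and about 5 points only in the least favourable corner of the assumed range.

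Nothing else turns on it. A lower event count does not by itself inflate the type I error, and the cutoff, sample size and test would stay as they are. At the analysis, SAP 8.1.1 already reports the actual number of IRC events, the reasons for censoring, and the hazard ratio with its confidence interval, which show the precision achieved better than a revised planning figure would. SAP 8.1.2 adds the agreement summary, the analysis of all IRC scans before crossover and the Investigator PFS test.

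This conclusion covers event numbers only. It rests on the design hazard ratio and on agreement of at least about 75%. Any bias from censoring at discordant local progressions is a separate question.

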12.7.2. Analyses for the Secondary Efficacy Endpoints

12.7.2.1. Overall Survival

Overall survival is defined as the time from date of randomization to the date of death due to any cause. Subjects who are alive at the analysis cutoff date will be censored at the date of last contact.

Assuming an HR of 0.67 for OS (median OS of 8 months in the placebo arm vs. 12 months in the AG-120 arm, assuming an exponential distribution), a total of 150 OS events will provide 64% power at a 1-sided alpha of 0.025. With a sample size of 186, additional OS follow-up of approximately 24 months after last subject is randomized will be needed to obtain 150 OS events. Assuming an HR of 0.615 (median OS of 8 months in the placebo arm vs. 13 months in the AG-120 arm, assuming an exponential distribution), a total of 150 OS events will provide 80% power at a 1-sided alpha of 0.025.

Due to the allowance of cross over of subjects who progress on the placebo arm to the AG-120 arm, it is anticipated that the true effect of AG-120 on survival as compared to placebo will not be able to be measured, and that the trial will not be powered to detect a meaningful survival effect.

OS will be compared between the two treatment arms, provided the primary endpoint PFS is statistically significant favoring the AG-120 arm. A hierarchical testing procedure will be adopted in this study and the OS analyses will be performed only if the primary efficacy endpoint PFS is statistically significant. OS will be analyzed based on the data from the ITT, according to the treatment arm to which subjects were randomized and the strata they were assigned at randomization. The distribution function of OS will be estimated using the Kaplan-Meier method. The median OS along with 95% CIs will be presented by treatment arm.

Assuming a proportional hazards model for OS, the null hypothesis will be tested:

$$H_{02} \text{ (null hypotheses): } \Theta_2 \geq 0 \text{ vs. } H_{a2} \text{ (alternative hypotheses): } \Theta_2 < 0$$

where Θ_2 is the log hazard ratio of OS in the AG-120 (investigational treatment) arm vs. placebo (control) arm.

Two analyses are planned for OS: 1) an interim analysis at the projected time of the final analysis for PFS (provided PFS is significant); 2) a final analysis for OS when 150 deaths are observed. Overall survival at the interim will be tested with the alpha being determined using the gamma spending function ($\gamma = -8$), and the overall type I error rate will be controlled at the 1-sided 0.025 level. The log-rank test stratified by randomization stratification factor will be used to compare OS between the two treatment arms. The unstratified log-rank test will also be conducted.

Kaplan-Meier estimates of OS will be presented for each treatment arm, including estimates of the median and other quantiles, as well as individual time points (eg, 3-month, 6-month, and 12-month rates). The HR of OS with 95% CI comparing AG-120 with placebo will be estimated from a Cox proportional hazards model stratified by randomization stratification factor.

Duration of follow-up will also be presented.

Sensitivity analyses for OS, such as taking into account the factor of cross over, will be specified in the SAP.

